12.6.1 Primary Analyses

12.6.1.1 Primary Biomarkers of Exposure in 24 hour collection

The primary BoExp (COHb in blood and urinary concentrations adjusted for creatinine of MHBMA, 3-HPMA and S-PMA) will be summarized as detailed in Section 12.1.3 “Descriptive Statistics”.

The baseline is as defined in Section 12.1.4 “Definitions for Statistical Data Analysis”,

The values and percent changes in the concentration adjusted for creatinine will be listed and summarized along with the COHb concentrations and percent changes from baseline. In addition line graphs will be produced for means (and 95% CI) over all timepoints.

For all arms the 24 hour urine collection will be collected daily from Day -1 to Day 5. Although the 24 hour urine collection will span into the following Day it will be reported by the day the collection started.

The primary endpoints will be log-transformed (base_e) prior to analysis. The analysis will compare (1) last Day 5 values of COHb in blood and (2) urinary concentrations of MHBMA, 3-HPMA and S-PMA corrected for creatinine on Day 5 between the THS 2.2 and CC arms. An ANCOVA (**Snedecor and Cochran 1982**) model will be used with terms for the log-transformed baseline value, sex, average daily CC consumption over the last 4 weeks as reported during screening and product.

The SAS code to be used is shown below:

```
Proc mixed data=_data_;
  Class product sex cigarette_cons;
  Model log (Day 5) = log (baseline) sex cigarette_cons product;
  Lsmean product / pdiff =control('CC') alpha=0.05 cl;
  Run;
```

The least squares (LS) means and estimate of the difference along with it's 95% CI will be back-transformed before presenting in the tables. The geometric LS means for each product along with the ratio (THS 2.2 : CC) and 95% CI will be presented in the tables.

The primary analysis will be performed on the FAS, with the PP Population used only to examine the robustness of the analysis of the primary endpoints.

In addition line graphs will be produced for product means (and 95% CI) over all timepoints for COHb in blood and urinary concentrations adjusted for creatinine of MHBMA, 3-HPMA and S-PMA.

The data will be presented in the below outputs, the TFL number refers to the TFL number in the accompanying TFL shell document:

TFL number	Title
FIGURES	
15.1.1.1	Blood COHb (%) Mean and 95% CI– FAS
15.1.1.2	MHBMA Urinary Concentration Adjusted for Creatinine (units) Mean and 95% CI – FAS
15.1.1.3	3-HPMA Urinary Concentration Adjusted for Creatinine (units) Mean and 95% CI– FAS
15.1.1.4	S-PMA Urinary Concentration Adjusted for Creatinine (units) Mean and 95% CI– FAS
15.1.1.5	Blood COHb (%) % Change from Baseline Mean and 95% CI– FAS
15.1.1.6	MHBMA Urinary Concentration Adjusted for Creatinine (units) % Change from Baseline Mean and 95% CI – FAS
15.1.1.7	3-HPMA Urinary Concentration Adjusted for Creatinine (units) % Change from Baseline Mean and 95% CI– FAS
15.1.1.8	S-PMA Urinary Concentration Adjusted for Creatinine (units) % Change from Baseline Mean and 95% CI– FAS
TABLES	
15.2.3.1.1	Analysis of Blood COHb (%) versus CC on Day 5 – FAS
15.2.3.1.2	Analysis of Blood COHb (%) versus CC on Day 5 – PP Population
15.2.3.2.1	Analysis of MHBMA Urinary Concentration Adjusted for Creatinine (units) versus CC on Day 5 – FAS
15.2.3.2.2	Analysis of MHBMA Urinary Concentration Adjusted for Creatinine (units) versus CC on Day 5 – PP Population
15.2.3.3.1	Analysis of 3-HPMA Urinary Concentration Adjusted for Creatinine (units) versus CC on Day 5 – FAS

TFL number	Title
15.2.3.3.2	Analysis of 3-HPMA Urinary Concentration Adjusted for Creatinine (units) versus CC on Day 5 – PP Population
15.2.3.4.1	Analysis of S-PMA Urinary Concentration Adjusted for Creatinine (units) versus CC on Day 5 – FAS
15.2.3.4.2	Analysis of S-PMA Urinary Concentration Adjusted for Creatinine (units) versus CC on Day 5 – PP Population
15.2.3.5	Descriptive Statistics of % Change in Primary Biomarkers of Exposure on Day 5 – FAS
15.2.3.5.1	Descriptive Statistics of % Change in Primary Biomarkers of Exposure on Day 5 by Sex – FAS
15.2.3.5.2	Descriptive Statistics of % Change in Primary Biomarkers of Exposure on Day 5 by Cigarette Consumption – FAS
15.2.3.6	Descriptive Statistics of Blood COHb (%) – FAS
15.2.3.6.1	Descriptive Statistics of Blood COHb (%) by Sex – FAS
15.2.3.6.2	Descriptive Statistics of Blood COHb (%) by Cigarette Consumption – FAS
15.2.3.7	Descriptive Statistics of MHBMA Urinary Concentration Adjusted for Creatinine (units) – FAS
15.2.3.7.1	Descriptive Statistics of MHBMA Urinary Concentration Adjusted for Creatinine (units) by Sex – FAS
15.2.3.7.2	Descriptive Statistics of MHBMA Urinary Concentration Adjusted for Creatinine (units) by Cigarette Consumption – FAS
15.2.3.8	Descriptive Statistics of 3-HPMA Urinary Concentration Adjusted for Creatinine (units) – FAS
15.2.3.8.1	Descriptive Statistics of 3-HPMA Urinary Concentration Adjusted for Creatinine (units) by Sex – FAS
15.2.3.8.2	Descriptive Statistics of 3-HPMA Urinary Concentration Adjusted for Creatinine (units) by Cigarette Consumption – FAS
15.2.3.9	Descriptive Statistics of S-PMA Urinary Concentration Adjusted for Creatinine (units) – FAS
15.2.3.9.1	Descriptive Statistics of S-PMA Urinary Concentration Adjusted for Creatinine (units) by Sex – FAS
15.2.3.9.2	Descriptive Statistics of S-PMA Urinary Concentration Adjusted for Creatinine (units) by Cigarette Consumption – FAS
LISTINGS	
15.3.3.1	Listing of Primary Biomarkers

The listing of the urinary biomarkers will include the concentration, the percent change in the concentration, the concentration adjusted for creatinine, the percent change in the concentration adjusted for creatinine, the volume of urine in the 24 hour collection, the quantity excreted over 24 hours and the percent change in quantity excreted over 24 hours.

The listing of the COHb data will include the concentration, the percent change in the concentration, and a flag for whether a subject's COHb is <2%.

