7.5.1 Biomarker of Exposure

7.5.1.1 Exhaled CO and Carboxyhemoglobin

Carboxyhemoglobin measured in blood and exhaled CO will be investigated as a measure of CO in all 3 study arms. The CO breath test should be conducted in timely conjunction with

the blood sampling for COHb, where applicable. In the SA arm, the CO breath test will serve as a verification of compliance (see Section 6.5.4).

Carbon Monoxide Breath Test

Carbon monoxide in exhaled breath will be measured using the Smokerlyzer[®] e.g. Micro+[™] Smokerlyzer[®] or similar device.

On Days -1 to Day 5, the CO breath test will be conducted 4 times per day. The first test should be conducted within 15 minutes prior to the first product use. The other 3 tests should be conducted as defined in section 9.

On Days 1 to Day 5, for subjects in the SA arm, the first CO breath test will be done between 08:00 AM and 10:00 AM. The other 3 tests should be conducted as defined in section 9.

On Day -2 and Day 6, the CO breath tests will be conducted once.

Carboxyhemoglobin

Assessment for COHb will be performed at the local laboratory. Carboxyhemoglobin in blood will be assessed on a daily basis, starting from Day -1 until Day 5.

On Day -1 to Day 4: one blood sample as defined in section 9.

On Day 5: one blood sample will be collected within 15 minutes prior to the first product use. The three other blood sample will be collected as defined in section 9.

For subjects in the SA arm, the first COHb will be done between 08:00 AM-10:00 AM. The three other blood samples will be collected as defined in section 9.

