| 12:00 PM-02:00 PM | | CO breath test | |
| before 3:00 PM | | Lunch | |
| 04:00 PM-06:00 PM | √ | CYP1A2 activity in plasma | 6 hours +/-15 minutes after intake of cup of coffee |
| 04:00 PM-06:00 PM | | CO breath test | |
| afternoon | | Snacks | |
| In the evening until 09:00 PM | | Dinner | |
| 08:00 PM-10:00 PM | | CO breath test | |
| 08:00 PM-10:00 PM | √ | COHb in blood | |
| 08:00 PM-10:00 PM | √ | Nicotine, cotinine in plasma | |
| 08:00 PM-11:00 PM | | HST questionnaire | |
| 08:00 PM- 11:00 PM | | MCEQ questionnaire (THS 2.2 and CC arms only), QSU-brief questionnaire | |
| 11:00 PM | | End of smoking period | |

Confidentiality statement: Data and information contained in this document are considered to constitute trade secrets and confidential commercial information, and the legal protections provided to such trade secrets and confidential information are hereby claimed under the applicable provisions of applicable law. No part of this document may be publicly disclosed without the written consent of Philip Morris Products S.A.

| Time | Blood sample | Procedures | Additional information |
|---------------------------|--------------|----------------------------|------------------------|
| Start of procedure | | Baseline Day 0 | |
| 6:30 AM-11:15 PM | | Collection of all CC butts | For accountability |

Abbreviations: AE = adverse event; BoExp = biomarkers of exposure; CAF = caffeine; CC = conventional cigarette(s); CO = carbon monoxide; COHb = carboxyhemoglobin; CYP1A2 = Cytochrome P450 1A2; CYP2A6 = Cytochrome P450 2A6; HST = human smoking topography; MCEQ = Modified Cigarette Evaluation Questionnaire; MNWS = Minnesota Nicotine Withdrawal Scale (revised version); QSU-brief = Questionnaire of Smoking Urges (brief version); SAE = serious adverse event; THS 2.2 = Tobacco Heating System 2.2; VAS = Visual analogue scale.

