12.1.4 Definitions for Statistical Data Analysis

The following definitions (Table 19) for statistical analyses/presentations will be used:

Table 19: Definition of terms for the statistical analysis

Term	Definition
Baseline Value	The last assessment prior to 06:29 AM on Day 1

N.B. For data where baseline is different to the above will be defined in the specific section of the SAP.

For urine collections taken on Days x to y, e.g., Days 5 to 6, these will be referred to as collected on Day x, i.e., Day 5, in the SAP.

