12.6.2 Secondary Analyses

12.6.2.1 Biomarkers of Exposure

In addition, the quantity excreted over 24 hours for MHBMA, 3-HPMA and S-PMA will be presented.

The primary BoExp will also be examined to compare the reductions in THS 2.2 vs. SA using the same methodology as for the primary analysis.

The secondary BoExp are exhaled CO, total 1-OHP in urine, total NNN in urine, 4-ABP in urine, 1-NA in urine, 2-NA in urine, o-tol in urine, CEMA in urine, HEMA in urine, B[a]P in urine, HMPMA in urine, S-BMA in urine, total NNAL in urine and NEQ in urine. The urine parameters will be expressed as concentrations adjusted for creatinine and the quantity excreted over 24 hours.

The baseline of the exhaled CO will be the time-matched measurements on Day 0, i.e. the 1st measurement on Days 1 to 5 will be matched to the 1st measurement on Day 0 and similarly for the 2nd, 3rd and 4th measurements. The baseline of the urinary biomarkers will be the last assessment prior to 06:29 AM on Day 1.

The values and percent changes for urinary BoExp in the quantity excreted over 24-hours and the concentration adjusted for creatinine will be listed and summarized. In addition line graphs will be produced for product means (and 95% CI) over all timepoints.

CO in exhaled breath will be measured using the Micro+™ Smokerlyzer® or similar device, conducted on Day -2 to Day 6. On Day -1 to Day 5 the first test per day will be performed within 15 minutes prior to the first product use and then between 12:00 and

02:00 PM, between 04:00 and 06:00 PM and between 08:00 and 10:00 PM. On Days -2 and Day 6 the CO breath tests will be conducted once.

Descriptive statistics summarized by exposure will be produced separately for all timepoints for all visits applicable for exhaled CO. This will be done on the FAS, stratified by sex, and CC consumption.

Actual values and percent changes from baseline in levels of exhaled CO will be listed and summarized. In addition line graphs will be produced for product means (and 95% CI) over all timepoints.

The last measurement of exhaled CO will be used in the analysis. An ANCOVA model will be used with terms for the baseline value, sex, average daily CC consumption over the last 4 weeks as reported during screening and product. No adjustment will be made for multiple comparisons.

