12.6.2.2 Nicotine and Cotinine Concentrations

The change from the Day 0 sample will be calculated for the Day 5 sample closest to 08:00 PM only. The concentrations of nicotine and cotinine will be listed and summarized along with this change. Line graphs of the nicotine and cotinine concentration profiles across all study days showing mean and 95% CI will also be produced.

For nicotine and plasma concentrations the change from baseline (Day 0 sample at 08:00 PM - 09:30 PM) on the Day 5 sample closest to 08:00 PM will be analyzed using an ANCOVA model with terms for baseline (Day 0) concentration, sex, average daily CC consumption over the last 4 weeks as reported during screening and product. No adjustment will be made for multiple comparisons.

The SAS code to be used is shown below:

```
Proc mixed data=_data_;
  Class product sex cigarette_cons time_point;
  Model change from baseline = baseline sex cigarette_cons product;
  Lsmean product / diff alpha=0.05 cl;
  Run;
```

LS means for each product along with the difference (THS 2.2 - CC) and 95% CI will be presented in the tables.

All figures, summaries and analyses will be performed on the FAS only.

The data will be presented in the below outputs, the TFL number refers to the TFL number in the accompanying TFL shell document:

TFL number	Title
FIGURES	
15.1.2.31	Plasma Nicotine Concentrations (ng/mL) Mean and 95% CI – FAS
15.1.2.32	Plasma Cotinine Concentrations (ng/mL) Mean and 95% CI – FAS
TABLES	
15.2.4.36	Descriptive Statistics of Plasma Nicotine Concentrations (ng/mL) – FAS
15.2.4.37	Descriptive Statistics of Plasma Cotinine Concentrations (ng/mL) – FAS
15.2.4.42	Analysis of Change from Day 0 Plasma Nicotine and Cotinine Concentrations at 08:00 PM on Day 5 – FAS
LISTINGS	
15.3.3.4	Listing of Plasma Nicotine Concentrations and Sampling Times
15.3.3.5	Listing of Plasma Cotinine Concentrations and Sampling Times

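### COHb has only an evening baseline, yet the SAP does not limit its percent change to evening samples, so the Day 5 pre-use value would show a spurious fall in the CC arm

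*SAP*

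**What the plan says.** Sampling: Protocol 7.5.1.1 states "On Day -1 to Day 4: one blood sample as defined in section 9", and the Day 0 schedule (Protocol Table 9) has the row "08:00 PM-10:00 PM | √ | COHb in blood". Day -1 (Table 8) is the same. SAP Table 16 gives a slightly wider window, to 11:00 PM, for Days -1 to 4, but that is still an evening sample. For Day 5, Protocol 7.5.1.1 adds: "On Day 5: one blood sample will be collected within 15 minutes prior to the first product use". The SA arm has its first Day 5 draw later in the morning. Further draws follow at 12:00-02:00 PM, 04:00-06:00 PM and 08:00-10:00 PM (Protocol Table 14).

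Baseline: SAP 12.1.4 defines it as "The last assessment prior to 06:29 AM on Day 1" and leaves exceptions to the specific sections. SAP 12.6.1.1 makes no exception for COHb, so its baseline is the Day 0 evening value.

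Outputs: SAP 12.6.1.1 has values "summarized along with the COHb concentrations and percent changes from baseline", asks for line graphs of means over all time points, and plans Figure 15.1.1.5, "Blood COHb (%) % Change from Baseline Mean and 95% CI". The COHb listing also carries percent change. For the ANCOVA the section names the last Day 5 COHb value. For percent change it names no sample.

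Elsewhere the SAP does deal with clock time. For exhaled CO, SAP 12.6.2.1 says "The baseline of the exhaled CO will be the time-matched measurements on Day 0". For plasma nicotine and cotinine, SAP 12.6.2.2 says "The change from the Day 0 sample will be calculated for the Day 5 sample closest to 08:00 PM only".

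**The concern.** The baseline sample follows a day of ad libitum smoking. The first Day 5 sample in the THS 2.2 and CC arms follows an overnight break, because smoking stops at 11:00 PM and restarts at 06:30 AM. Setting one against the other mixes product effect with time of day. A CC subject whose smoking never changed would appear to have cut CO exposure.

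The report could also disagree with itself. Protocol 7.5.1.1 asks for the breath test and the COHb draw to be taken close together. The Day 5 morning exhaled CO would be compared with a Day 0 morning value, while COHb from about the same moment would be compared with a Day 0 evening value.

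COHb is one of four primary biomarkers, and Day 5 percent change in the primary biomarkers, overall and by sex and cigarette consumption, is among the topline outputs in SAP 13.3. Readers of those outputs need to know which Day 5 sample is shown.

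**Working it through.** The documents state no figure for a morning COHb change, so there is none to reproduce. The check below sizes the artefact.

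**Inputs**
- Overnight break: last smoking 11:00 PM, earliest pre-use draw 06:15 AM (15 minutes before 06:30 AM), so 7.25 h.
- CC evening level: set to 1, with no true change over the study.
- THS 2.2 evening level: 0.40 of CC (Protocol Table 16, SAP Table 11).
- Abstinence floor: the same table gives THS 2.2/SA = 2.10, so SA/CC = 0.40/2.10 = 0.19.
- Half-life: **assumed**, 3-8 h. Protocol 4.2 says only that the primary biomarkers average 24 h or less, so 24 h is shown as the bound.

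**Formulas**
- Morning level = 0.19 + (evening level - 0.19) x 0.5^(7.25/half-life)
- Percent change = 100 x (morning level - 1), following SAP Section 7

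Example, CC at 4 h: 0.5^(7.25/4) = 0.285; 0.19 + 0.81 x 0.285 = 0.42; change = -58%. THS 2.2 at 4 h: 0.19 + 0.21 x 0.285 = 0.25; change = -75%, against a true -60%.

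| Half-life (h) | CC change (true 0%) | THS 2.2 change (true -60%) | False part in THS 2.2 (points) | Morning THS 2.2:CC (evening 0.40) |
|---|---|---|---|---|
| 3 | -66% | -77% | 17 | 0.67 |
| 4 | -58% | -75% | 15 | 0.59 |
| 5 | -51% | -73% | 13 | 0.55 |
| 6 | -46% | -72% | 12 | 0.52 |
| 8 | -38% | -70% | 10 | 0.49 |
| 24 | -15% | -64% | 4 | 0.43 |

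SA sits at the floor throughout: 0.19 - 1 = -81%, equal to its true change at every half-life.

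**Effect on the contrast.** In the evening, CC and THS 2.2 are 60 points apart (0% and -60%). In the morning at 4 h they are 75 - 58 = 17 points apart, and at 6 h 72 - 46 = 26 points.

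**Other Day 5 samples.** The midday and afternoon draws also lack a matching baseline. They fall within smoking hours, and the documents give nothing from which to size their mismatch.

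**Primary test.** The ANCOVA in SAP 12.6.1.1 takes the last Day 5 value (evening) with the Day 0 evening baseline as covariate, so the clock times agree.

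**The case against.** The strongest reply is that nothing inferential depends on this. The confirmatory comparison is evening against evening and between arms, and COHb levels are also displayed by arm. SAP Section 9 plans a product-by-time-point COHb model with least squares means at each time point, which would allow same-time comparisons. This stands, and it limits the point to descriptive reporting.

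A second reply is that no sentence says outright that percent change will be computed at all four Day 5 draws. Table 15.2.3.5 refers only to Day 5 and combines COHb with urinary markers that have one Day 5 value each. The one COHb value singled out in 12.6.1.1 is the last, and the table shells are in a separate document. This stands in part. Inclusion of all four is the natural reading, since no sample is excluded and the graphs cover all time points, but for Tables 15.2.3.5 and 15.2.3.6 it remains a reading. The ambiguity itself needs settling.

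A third reply is that the size depends on a half-life the documents do not give. That is correct, hence the range. The direction in the CC arm does not depend on it.

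Section 9 is not a full answer. It makes the comparison over all time points the main one, whereas 12.6.1.1 uses the last Day 5 value and its model has no time-point term. If the morning sample entered an all-time-point comparison, the THS 2.2:CC ratio would be pulled toward 1.

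**Conclusion.** The point holds for descriptive outputs: Figure 15.1.1.5, the COHb listing, and Tables 15.2.3.5 and 15.2.3.6 if they include the non-evening samples. The spurious CC fall at the Day 5 pre-use sample is about -46% to -58% for an assumed 4-6 h half-life, -38% to -66% for 3-8 h, and -15% at the 24 h bound. These figures assume simple exponential decay to the floor implied by the planning ratios, a level at 11:00 PM equal to the evening value, and a draw at 06:15 AM.

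Four stronger inferences are not supported:
- **A false reduction in every arm.** SA subjects have been abstinent since Day 1 and have no overnight smoking washout, so their fall is real. In THS 2.2 most of the fall is real.
- **Flattery of THS 2.2.** Overnight decay lowers CC more than THS 2.2, so the artefact narrows the contrast.
- **A CC artefact that passes the success criterion.** The 50% criterion is a THS 2.2 to CC comparison, which a within-arm change can neither meet nor fail. The artefact is also below 50% for part of the assumed range.
- **A fall of about -57% to -72% at 4-6 h.** That follows only if COHb decays to zero, which contradicts the abstinence floor in the planning ratios.

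The primary ANCOVA and the success decision are unaffected as 12.6.1.1 is written. The change is worth making because COHb is a primary biomarker, some of these outputs are topline, and the remedy is nearly free.

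**What to change.** In SAP 12.6.1.1, limit COHb percent change from baseline to the 08:00-10:00 PM sample on Days 1-5, in line with the rule SAP 12.6.2.2 applies to plasma nicotine. Apply this to Figure 15.1.1.5, Tables 15.2.3.5 and 15.2.3.6, the listing and the matching topline tables, and align the evening window in SAP Table 16 with the protocol. Report the Day 5 pre-use, midday and afternoon samples as levels by arm, with THS 2.2:CC ratios at the same time point. Time matching as for exhaled CO is not available, because Day 0 has no COHb draw at those times.

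Also reconcile Section 9 with 12.6.1.1: state which COHb comparison is the main one and how the three unmatched Day 5 samples enter any model over time points.

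The cost is a sentence on percent change, a clarification of Section 9, and edits to the table shells, with no new data. The downside is that no within-subject percent change is shown for three of the four Day 5 samples.

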12.6.1.2 Confirmatory Analysis

The hypothesis to be tested for each of the primary BoExp is that the geometric mean level on Day 5 of the BoExp for THS 2.2 is lower relative to CC.

Analysis of the primary BoExp will be conducted on the natural log scale. In order to test the follow hypothesis

$$\begin{aligned} \text{Null hypothesis (H}_0\text{):} & \quad m_1 \geq m_2 \\ \text{Alternative hypothesis (H}_1\text{):} & \quad m_1 < m_2 \end{aligned}$$

Where m_1 and m_2 are the geometric means of the BoExp levels on Day 5 for THS 2.2 and CC respectively.

The SAS code will be the same as described in Section 12.6.1.1 “Primary Biomarkers of Exposure in 24 hour collection”.

The confirmatory analysis will be performed on the FAS only.

12.6.2 Secondary Analyses

12.6.2.1 Biomarkers of Exposure

In addition, the quantity excreted over 24 hours for MHBMA, 3-HPMA and S-PMA will be presented.

The primary BoExp will also be examined to compare the reductions in THS 2.2 vs. SA using the same methodology as for the primary analysis.

The secondary BoExp are exhaled CO, total 1-OHP in urine, total NNN in urine, 4-ABP in urine, 1-NA in urine, 2-NA in urine, o-tol in urine, CEMA in urine, HEMA in urine, B[a]P in urine, HMPMA in urine, S-BMA in urine, total NNAL in urine and NEQ in urine. The urine parameters will be expressed as concentrations adjusted for creatinine and the quantity excreted over 24 hours.

The baseline of the exhaled CO will be the time-matched measurements on Day 0, i.e. the 1st measurement on Days 1 to 5 will be matched to the 1st measurement on Day 0 and similarly for the 2nd, 3rd and 4th measurements. The baseline of the urinary biomarkers will be the last assessment prior to 06:29 AM on Day 1.

The values and percent changes for urinary BoExp in the quantity excreted over 24-hours and the concentration adjusted for creatinine will be listed and summarized. In addition line graphs will be produced for product means (and 95% CI) over all timepoints.

CO in exhaled breath will be measured using the Micro+™ Smokerlyzer® or similar device, conducted on Day -2 to Day 6. On Day -1 to Day 5 the first test per day will be performed within 15 minutes prior to the first product use and then between 12:00 and

02:00 PM, between 04:00 and 06:00 PM and between 08:00 and 10:00 PM. On Days -2 and Day 6 the CO breath tests will be conducted once.

Descriptive statistics summarized by exposure will be produced separately for all timepoints for all visits applicable for exhaled CO. This will be done on the FAS, stratified by sex, and CC consumption.

Actual values and percent changes from baseline in levels of exhaled CO will be listed and summarized. In addition line graphs will be produced for product means (and 95% CI) over all timepoints.

The last measurement of exhaled CO will be used in the analysis. An ANCOVA model will be used with terms for the baseline value, sex, average daily CC consumption over the last 4 weeks as reported during screening and product. No adjustment will be made for multiple comparisons.

The analysis will compare the log-transformed urinary concentrations corrected for creatinine on Day 5 to 6 and the quantity excreted over 24-hours on Day 5 to 6 between the THS 2.2 and CC arms. An ANCOVA model will be used with terms for the log-transformed baseline value, sex, average daily CC consumption over the last 4 weeks as reported during screening and product. No adjustment will be made for multiple comparisons.

The SAS code will be the same as described in Section 12.6.1.1 “Primary Biomarkers of Exposure in 24 hour collection”.

LS means for each product along with the difference (THS 2.2 - CC) and 95% confidence interval (CI) will be presented in the tables.

The secondary BoExp will also be examined to compare the reductions in THS 2.2 vs. SA using the same methodology as above.

TFL number	Title
FIGURES	
15.1.2.1	Urinary MHBMA Quantity Excreted Over 24 hours Mean and 95% CI– FAS
15.1.2.2	Urinary 3-HPMA Quantity Excreted Over 24 hours Mean and 95% CI– FAS
15.1.2.3	Urinary SPMA Quantity Excreted Over 24 hours Mean and 95% CI– FAS
15.1.2.4	Exhaled CO Arithmetic Mean and 95% CI– FAS
15.1.2.5	1-OHP Urinary Concentration Adjusted for Creatinine Mean and 95% CI– FAS
15.1.2.6	Urinary 1-OHP Quantity excreted Over 24 hours Mean and 95% CI– FAS

TFL number	Title
15.1.2.7	Total NNN Urinary Concentration Adjusted for Creatinine Mean and 95% CI- FAS
15.1.2.8	Urinary Total NNN Quantity Excreted Over 24 hours Mean and 95% CI- FAS
15.1.2.9	4-ABP Urinary Concentration Adjusted for Creatinine Mean and 95% CI- FAS
15.1.2.10	Urinary 4-ABP Quantity Excreted Over 24 hours Mean and 95% CI- FAS
15.1.2.11	1-NA Urinary Concentration Adjusted for Creatinine Mean and 95% CI- FAS
15.1.2.12	Urinary 1-NA Quantity Excreted Over 24 hours Mean and 95% CI- FAS
15.1.2.13	2-NA Urinary Concentration Adjusted for Creatinine Mean and 95% CI- FAS
15.1.2.14	Urinary 2-NA Quantity Excreted Over 24 hours Mean and 95% CI- FAS
15.1.2.15	o-tol Urinary Concentration Adjusted for Creatinine Mean and 95% CI- FAS
15.1.2.16	Urinary o-tol Quantity Excreted Over 24 hours Mean and 95% CI- FAS
15.1.2.17	CEMA Urinary Concentration Adjusted for Creatinine Mean and 95% CI- FAS
15.1.2.18	Urinary CEMA Quantity Excreted Over 24 hours Mean and 95% CI- FAS
15.1.2.19	HEMA Urinary Concentration Adjusted for Creatinine Mean and 95% CI- FAS
15.1.2.20	Urinary HEMA Quantity Excreted Over 24 hours Mean and 95% CI- FAS
15.1.2.21	B[a]P Urinary Concentration Adjusted for Creatinine Mean and 95% CI- FAS
15.1.2.22	Urinary B[a]P Quantity Excreted Over 24 hours Mean and 95% CI- FAS
15.1.2.23	3-HMPMA Urinary Concentration Adjusted for Creatinine Mean and 95% CI- FAS
15.1.2.24	Urinary 3-HMPMA Quantity Excreted Over 24 hours Mean and 95% CI- FAS
15.1.2.25	S-BMA Urinary Concentration Adjusted for Creatinine Mean and 95% CI- FAS
15.1.2.26	Urinary S-BMA Quantity Excreted Over 24 hours Mean and 95% CI- FAS
15.1.2.27	Total NNAL Urinary Concentration Adjusted for Creatinine Mean and 95% CI- FAS
15.1.2.28	Urinary Total NNAL Quantity Excreted Over 24 hours Mean and 95% CI- FAS
15.1.2.29	NEQ Urinary Concentration Adjusted for Creatinine Mean and 95% CI- FAS
15.1.2.30	Urinary NEQ Quantity Excreted Over 24 hours Mean and 95% CI- FAS

TFL number	Title
TABLES	
15.2.4.1	Analysis of Primary Biomarkers of Exposure versus SA on Day 5 – FAS
15.2.4.2	Analysis of Urinary Quantity Excreted of MHBMA, 3-HPMA and S-PMA over 24 hours on Day 5 – FAS
15.2.4.3	Descriptive Statistics of Urinary Quantity Excreted of MHBMA over 24 hours (units) – FAS
15.2.4.4	Descriptive Statistics of Urinary Quantity Excreted of 3-HPMA over 24 hours (units) – FAS
15.2.4.5	Descriptive Statistics of Urinary Quantity Excreted of S-PMA over 24 hours (units) – FAS
15.2.4.6	Analysis of Exhaled CO (ppm) on Day 5 – FAS
15.2.4.7	Descriptive Statistics of Exhaled CO (ppm) – FAS
15.2.4.8	Descriptive Statistics of Time Matched Changes (%) in Exhaled CO – FAS
15.2.4.9	Analysis of Urinary 1-OHP on Day 5 – FAS
15.2.4.10	Descriptive Statistics of Urinary 1-OHP – FAS
15.2.4.11	Analysis of Urinary Total NNN on Day 5 – FAS
15.2.4.12	Descriptive Statistics of Urinary Total NNN – FAS
15.2.4.13	Analysis of Urinary 4-ABP on Day 5 – FAS
15.2.4.14	Descriptive Statistics of Urinary 4-ABP – FAS
15.2.4.15	Analysis of Urinary 1-NA on Day 5 – FAS
15.2.4.16	Descriptive Statistics of Urinary 1-NA – FAS
15.2.4.17	Analysis of Urinary 2-NA on Day 5 – FAS
15.2.4.18	Descriptive Statistics of Urinary 2-NA – FAS
15.2.4.19	Analysis of Urinary o-tol on Day 5 – FAS
15.2.4.20	Descriptive Statistics of Urinary o-tol – FAS
15.2.4.21	Analysis of Urinary CEMA on Day 5 – FAS
15.2.4.22	Descriptive Statistics of Urinary CEMA – FAS
15.2.4.23	Analysis of Urinary HEMA on Day 5 – FAS
15.2.4.24	Descriptive Statistics of Urinary HEMA – FAS
15.2.4.25	Analysis of Urinary B[a]P on Day 5 – FAS
15.2.4.26	Descriptive Statistics of Urinary B[a]P – FAS
15.2.4.27	Analysis of Urinary HMPMA on Day 5 – FAS
15.2.4.28	Descriptive Statistics of Urinary HMPMA – FAS
15.2.4.29	Analysis of Urinary S-BMA on Day 5 – FAS
15.2.4.30	Descriptive Statistics of Urinary S-BMA – FAS
15.2.4.31	Analysis of Urinary Total NNAL on Day 5 – FAS
15.2.4.32	Descriptive Statistics of Urinary Total NNAL – FAS
15.2.4.33	Analysis of Urinary NEQ on Day 5 – FAS
15.2.4.34	Descriptive Statistics of Urinary NEQ – FAS
LISTINGS	
15.3.3.2	Listing of Secondary Biomarkers and Sampling / Collection Times

